# 6.2 Secondary Outcome Variables

# 6.2.1 Efficacy

### Stage 1 and Stage 2

The slope of the change in log10LAM pg/mL values and the change in time to detection (TTD) in the Mycobacteria Growth Indicator Tube® (MGIT) system will be assessed from baseline to Day 14.

#### Stage 2

Efficacy will be assessed by the change in bacterial load in sputum as a measure of EBA. Bacterial load in sputum at each collection time point will be measured by CFU counts on agar media. The EBA will be measured as the slope of the change in log10CFU/mL from baseline (baseline is the log10 of the mean of the values from Day -2 and Day -1 with more details in Section 8.1) to Day 14 and compared with the administration of 30 mg OPC-167832 alone (data derived from Stage 1). Similar analyses are performed for log10LAM pg/mL and MGIT TTD endpoints.

#### 6.2.2 Pharmacokinetics

#### Stage 1

Plasma concentrations of rifampin and isoniazid at 2 and 6 hours postdose will be determined for compliance.

#### Stage 2

The following PK parameters will be determined for plasma DM-6705 (metabolite of delamanid) and M2 (metabolite of BDQ):

- Day 1:  $C_{max}$ ,  $t_{max}$ , and  $AUC_t$ .
- Day 14:  $C_{\text{max,ss}}$ ,  $t_{\text{max}}$ ,  $t_{1/2,z}$ , and  $AUC_t$ .

Plasma concentrations of rifampin and isoniazid at 2 and 6 hours postdose will be determined for compliance.

# 6.2.3 Pharmacokinetics/Pharmacodynamics - Stage 1 and Stage 2

The maximum effect and EC80 for OPC-167832, regardless of dose level, will be determined from an exposure-response analysis of the results from the Otsuka TB ELISA LAM. The results can be found in a separate population PK/PD analysis report.

Statistical Analysis Plan

The relationship between QT interval and plasma concentrations of OPC-167832 (stage 1) and OPC-167832 when administered with delamanid and/or BDQ (Stage 2) will be evaluated. The results can be found in a separate population PK/PD analysis report.

# 6.2.4 Safety and Tolerability - Stage 1 and Stage 2

Safety and tolerability of OPC-167832 when administered with delamanid and/or BDQ (data derived from stage 2) will be compared with the administration of OPC-167832 alone (data derived from stage 1). Safety and tolerability will be assessed based on the incidence of AEs and the incidence of abnormal findings in clinical laboratory tests (serum chemistry, hematology, urinalysis, and coagulation), vital signs, ECGs and physical examinations.

# 7 Disposition and Demographic Analysis

# 7.1 Subject Disposition

Number of patients screened, randomized, included in safety analysis or efficacy analysis, completed, early terminated will be summarized by count and percentage within each treatment group. Enrolment by country and by age group will also be summarized.

The frequency and percentages will be presented by treatment groups for Stage 1, and Stage 2 with a combined RHEZ group from Stage 1 and Stage 2.

# 7.2 Demographic and Baseline Characteristics

Summary statistics (mean, standard deviation, median, minimum and maximum) will be presented for continuous baseline characteristics. Frequency and percentage of discrete baseline variables will also be presented. Summaries will be presented by treatment groups based on the Randomized Analysis Set.

Demographic and baseline characteristics variables include:

- Age
- Sex
- Race
- Ethnicity
- Weight, Height, BMI
- Baseline CFU/mL count (Actual X1000)
- Baseline CFU/mL count (log10)

- Baseline x-ray
- Baseline HIV Screen
- Baseline FSH
- Baseline Urine/Blood alcohol
- Baseline Urine test for isoniazid (only applicable to protocol dated 26 Feb 2018)

The baselines for lab tests, ECG, vital sign and overnight sputum culture results are summarized with post-baseline results and will be described in later sections.

The analysis will be presented by treatment groups for Stage 1, and Stage 2 with a combined RHEZ group from Stage 1 and Stage 2.

# 7.3 Medical History

Medical history will be presented by count and frequency for each system organ class and preferred term for each treatment group. The summary will be based on the Randomized Analysis Set.

The frequencies and percentages will be presented by treatment groups for Stage 1, and Stage 2 with a combined RHEZ group from Stage 1 and Stage 2.

# 7.4 Treatment Compliance

Plasma concentrations of rifampin and isoniazid at 2 and 6 hours postdose will be determined for compliance. The time and dose of IMP and RHEZ administration during the trial will be recorded in eCRF and be listed. No analysis will be performed on compliance.

#### 7.5 Prior and Concomitant Medication

The proportion of subjects taking concomitant medications will be tabulated by drug classification using the WHO drug dictionary WHODRUG B3G March 2019 for Safety Analysis Set. Concomitant medications taken prior to the study medication treatment period, during study medication treatment period and after the study treatment will be tabulated. The study medication treatment period is defined as days from first IMP till the last dose of OPC-167832 and/or delamanid and/or bedaquiline in non-RHEZ groups. For RHEZ group, Day 14 (study date – first RHEZ date +1) is used as end point for "IMP dosing period" period. Concomitant medications will be listed. Anti-TB concomitant medications and other general concomitant medications will be summarized separately.

The analysis will be presented by treatment groups for Stage 1, and Stage 2 with a combined RHEZ group from Stage 1 and Stage 2.

Statistical Analysis Plan

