
On Day 20 (or at ET), the following will be performed:
 
 
• Perform a targeted physical examination.
 
• Measure weight.
 
• Assess vital signs (blood pressure, heart rate, temperature, and respiratory rate). Vital signs will be obtained after the subject has been at rest in the supine position for at least 1 minute.
 
• Collect serum chemistry, hematology, urinalysis, and coagulation clinical laboratory samples.
 
• For subjects randomized to OPC-167832 (stage 1) and/or delamanid and/or BDQ (stage 2), collect a PK blood sample for OPC-167832 only (stage 1) or OPC-167832, delamanid and its metabolite DM-6705, or BDQ and its metabolite M2 (stage 2) at 144 hours after the Day 14 dose.b
 
• Administer treatment for pulmonary TB to all subjects according to the local standard of care regimen (RHEZ).
 
• After completion of the inpatient stay, all subjects must be referred to local community clinics to receive continued treatment for pulmonary TB per the local standard of care regimen.
 
• Provide meals as needed.
 
• Discharge subjects from the trial site.
 

Follow-up (14 ± 3 Days After the Last Dose of Trial Treatment [IMP or RHEZ])
Contact the subjects via telephone for follow-up of AEs and concomitant medication.
Throughout the Trial

The following will be performed from the screening visit through and during the follow-up telephone call:
 
 
• Assess and record AEs
 
• Record prior/concomitant medications (including current oral antipsychotic medication), as applicable.
 

Protocol 323-201-00003

aIn subjects with no clinical indication to start RHEZ immediately, commencement of RHEZ can be delayed for up to 3 days (Days 15, 16, or 17) under close supervision in the trial site hospital ward

bThe Day 20 PK sample will be collected during the ET visit.

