#### 3.2.2 Reference Product

# 3.2.2.1 Stage 1 and Stage 2

Subjects randomized to RHEZ will receive QD oral doses of RHEZ from Day 1 through Day 20.

Subjects will receive Rifafour® single-dose combination tablets. Each RHEZ tablet contains 150 mg rifampicin, 75 mg isoniazid, 400 mg pyrazinamide, and 275 mg ethambutol. Subjects will receive the following number of Rifafour tablets per day based on their pretreatment body weight:

- Subjects weighing 30 to 37 kg will receive 2 tablets per day.
- Subjects weighing 38 to 54 kg will receive 3 tablets per day.
- Subjects weighing 55 to 70 kg will receive 4 tablets per day.
- Subjects weighing > 70 kg will receive 5 tablets per day.

RHEZ will be administered with 240 mL of still (noncarbonated) water 1 hour prior to a meal or 2 hours after a meal.

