### 9.1 Extent of Exposure

In Stage 1, subjects randomized to OPC-167832 will receive once daily oral doses of IMP (OPC-167832) from Day 1 through Day 14. After Day 14, the subjects will receive treatment for pulmonary TB according to the local standard of care regimen (RHEZ). In subjects with no clinical indication to start RHEZ immediately, commencement of RHEZ can be delayed for up to 3 days (Days 15, 16, and 17) under close supervision in the trial site hospital ward. Subjects randomized to RHEZ will receive once daily oral doses of RHEZ from Day 1 through Day 20.

In Stage 2, subjects randomized to IMP (OPC-167832 and/or delamanid and/or BDQ) will receive once daily oral doses of IMP from Day 1 through Day 14. After Day 14, the subjects will receive treatment for pulmonary TB according to the local standard of care regimen (RHEZ). In subjects with no clinical indication to start RHEZ immediately, commencement of RHEZ can be delayed for up to 3 days (Days 15, 16, and 17) under close supervision in the trial site hospital ward. Subjects randomized to RHEZ will receive once daily oral doses of RHEZ from Day 1 through Day 20.

Exposure to IMP is considered to be the exposure of OPC, DLM or BDQ (for the three OPC-containing regimens) in study days 1-14. For comparison purposes, for the RHEZ arm also, exposure to IMP will be taken to be the exposure to any treatment with RHEZ in days 1-14, and will be tabulated for the first 14 days only. The total exposure to IMP or reference product (RHEZ) in days will be divided to time intervals (No exposure, 1-2 days, 3-4 days, etc.) and the number and percentage of patients whose durations of exposure are in each interval will be presented for each treatment group. The duration of exposure is calculated as the last date of IMP (within 14 study days) – first date of IMP +1. For patients who are lost to follow-up, the last known date of taking IMP or RHEZ (within 14 study days) will be used for missing last date.

Patients randomized to RHEZ will receive once daily oral doses of RHEZ from Day 1

through Day 20. For the RHEZ group, the exposure table will summarize the exposure to RHEZ within the first 14 days of treatment only

All analyses will be presented by treatment groups for Stage 1, and Stage 2 with a combined RHEZ group from Stage 1 and Stage 2.

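### SAP 7.5 ends the concomitant-medication window at the last dose in the IMP arms but at a fixed Day 14 in the RHEZ arm, with no provision for RHEZ subjects who stop before Day 14

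*SAP*

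**What the plan says.** SAP 7.5 reports the proportion of subjects in the Safety Analysis Set taking each drug class, split by period: "Concomitant medications taken prior to the study medication treatment period, during study medication treatment period and after the study treatment will be tabulated". Anti-TB drugs are summarised separately from other medication.

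For the arms containing OPC-167832, the treatment period is "days from first IMP till the last dose of OPC-167832 and/or delamanid and/or bedaquiline in non-RHEZ groups". That is a date specific to each subject.

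For the reference arm the rule is different: "For RHEZ group, Day 14 (study date – first RHEZ date +1) is used as end point for" what the section at that point calls the IMP dosing period. It does not mention the last RHEZ dose, and no other end rule for RHEZ appears in the section. The two end points stand next to each other in the text: "the last dose of OPC-167832 and/or delamanid and/or bedaquiline in non-RHEZ groups. For RHEZ group, Day 14".

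The reason for a Day 14 limit is clear from SAP 3.2.2.1: "Subjects randomized to RHEZ will receive QD oral doses of RHEZ from Day 1 through Day 20". Without a limit the RHEZ window would be six days longer than the planned 14-day IMP window.

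SAP 9.1 applies the same 14-day limit to exposure: "for the RHEZ arm also, exposure to IMP will be taken to be the exposure to any treatment with RHEZ in days 1-14". There, though, the limit is combined with actual dosing: "The duration of exposure is calculated as the last date of IMP (within 14 study days"), less the first date, plus one.

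**The concern.** The two kinds of arm are windowed by different rules whenever a subject stops early. A reader would use the *during* columns to see which other drugs overlapped randomised treatment, and would use the separate anti-TB summary to see whether other anti-TB drugs did. For a RHEZ subject who stops before Day 14, the *during* column can include drugs first taken after randomised treatment had ended. For an IMP subject with the same history, those drugs appear only under *after*. The columns would then not mean the same thing across arms, and SAP 7.5 and SAP 9.1 would disagree about how long the same RHEZ subject was on treatment.

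**Working it through.** The plan gives no figure to reproduce, so the check is a comparison of rules and some simple arithmetic.

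**Inputs**
- End of window, IMP arms: the subject's last dose (SAP 7.5).
- End of window, RHEZ arm: study Day 14 counted from first RHEZ (SAP 7.5).
- Exposure end, both kinds of arm: last dosing date within 14 study days (SAP 9.1).
- Early permanent discontinuation of either IMP or RHEZ is foreseen (Protocol 3.8.3.1).
- Follow-up call: 14 (± 3) days after the last dose of trial treatment (Protocol Table 3.7-1, footnote c).
- Planned RHEZ subjects: 4 in each of 4 Stage 1 cohorts and 4 in Stage 2 (SAP 3.1.1, 3.1.2).

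**Windows for a subject whose last randomised dose is on Day d, with d < 14**

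| Arm and rule | *During* window | Off-treatment days labelled *during* |
|---|---|---|
| IMP, SAP 7.5 | Days 1 to d | 0 |
| RHEZ, SAP 7.5 | Days 1 to 14 | 14 − d |
| RHEZ, if the SAP 9.1 rule were used | Days 1 to d | 0 |

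The quantity 14 − d is 13 at d = 1, 9 at d = 5, 4 at d = 10 and 1 at d = 13. It gives the length of the interval in which a medication can be placed in the wrong period. It is not itself tabulated, since the table counts subjects.

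**Can such medication be recorded?** The protocol plans a final contact: "Contact the subjects via telephone for follow-up of AEs and concomitant medication". It falls between Day d + 11 and Day d + 17, with a target of Day d + 14.
- At the target, the call is on or after Day 14 for every d ≥ 1.
- At the earliest allowed call, d + 11 ≥ 14 requires d ≥ 3.

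So the interval can be covered. Recording is not assured: Table 3.7-1 and Table 3.7.3-1 ask for concomitant medication through the end of participation, but Protocol 3.7.4 limits recording after the evaluation period to drugs that treat or caused an adverse event.

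**Effect on a tabulated percentage.** Planned RHEZ denominators are 4 × 4 = 16 in Stage 1 and 16 + 4 = 20 combined. Suppose one RHEZ subject stops early and first takes a drug class between Day d + 1 and Day 14:
- Stage 1 RHEZ, *during*: 1/16 = 6.25, or about 6.3 percentage points.
- Combined RHEZ, *during*: 1/20 = 5.0 percentage points.
- Same event in an IMP arm of 14: 0 points in *during*; 1/14 = 7.1 points in *after*.

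If the subject had already taken that class before stopping, the *during* count does not change. If no RHEZ subject stops before Day 14, no cell changes.

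**The case against.** The strongest reply is that Day 14 was meant only as a cap on a drug planned to Day 20, and that SAP 7.5 simply omits the early stopper. That is a plausible account of intent, and the cap should stay. It does not rescue the text. The section states an end point for the RHEZ group without condition, a programmer following it would produce the unequal windows, and SAP 9.1 shows that the cap and the last dose can be combined.

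The SAP 9.1 contrast has one loose end. It refers to any treatment with RHEZ in the first 14 days, which could be read to include RHEZ continued as local care after withdrawal. The contrast is clean for randomised dosing, and the corrected wording should say so.

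A reader might infer more than the documents support, in three ways.
- *That the reference arm will look contaminated by other anti-TB drugs.* The local standard of care is itself RHEZ, and SAP 9.1 places RHEZ dosing in the anti-TB concomitant medication listing. A subject who leaves early and continues the same drugs would probably add no new class, although the table shells are not available to confirm this. A switch to a different drug before Day 14 would be needed.
- *That misplaced entries will certainly occur.* Stopping treatment ends trial participation (Protocol 3.8.3.1), Protocol 3.7.4 narrows later recording, and dosing is inpatient with hand and mouth checks (Protocol 3.12). The documents give no discontinuation rate for RHEZ.
- *That the comparison with RHEZ is biased in an inferential sense.* No formal comparison of concomitant medication is planned, and this window feeds no efficacy, safety or PK estimate.

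It is also fair that the subject listings of medication and of dosing times (SAP 7.4, 7.5) would let a careful reader trace any misplaced entry among about 20 RHEZ subjects.

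**Conclusion.** The inconsistency stands as a small error in the rule as written. SAP 7.5 treats early stoppers differently by arm, and SAP 9.1 handles the same situation another way. The consequence is limited to a descriptive table: up to 6.3 points (Stage 1 RHEZ) or 5.0 points (combined RHEZ) in a drug-class row for each RHEZ subject affected. Those figures assume planned denominators, which subject replacement (Protocol 3.3.2) could change. They also require that a RHEZ subject stops before Day 14, that a drug class new to that subject is first taken by Day 14, and that it is recorded. If any of these fails, the effect is zero. Nothing here bears on the EBA analyses or on the choice of a 14-day comparison period.

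**What to change.** In SAP 7.5, define the end of the RHEZ *during* period as the earlier of the subject's last randomised RHEZ dose and study Day 14, where study Day 14 is counted from the first RHEZ date as now. The word *randomised* keeps RHEZ given as local care after withdrawal from extending the window. It would help to use one name for the period throughout the section.

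The change keeps the 14-day cap, leaves every subject dosed through Day 14 unchanged, applies a last-dose rule to all arms, and agrees with SAP 9.1. For an early RHEZ stopper, the off-treatment days labelled *during* fall from 14 − d to 0, and medication first taken after stopping is tabulated as *after*. The cost is one SAP sentence and one line of programming, with no change to data collection.

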#### 7.6 Protocol Deviations

Frequency of protocol deviations (PDs) collected from CRF will be summarized by type of deviation (e.g., deviations in entry criteria, dosing, prohibited concomitant medication, procedural, met withdrawal criteria but was not withdrawn). The analysis will be presented by treatment group for Stage 1, and Stage 2 with a combined RHEZ group from Stage 1 and Stage 2. In addition, a subject listing for non-COVID-19 related PDs will be provided. COVID-19 related PDs will be listed separately.

# 8 Efficacy Analyses

# 8.1 Primary Efficacy Endpoint Analyses

# 8.1.1 Stage 1

Overnight sputum will be collected starting from 3pm to 7am next day starting on Day -2, -1, 2, 4, 6, 8, 10, 12 and Day 14. *Mycobacterium tuberculosis* bacterial load in sputum at each collection time point will be measured by CFU counts on solid media culture. Two agar media bi-plates will be inoculated with 0.1 mL sputum sample per side (total of 0.2 ml per whole plate) at each visit. Each sample was diluted to  $1,10^{-1},10^{-2},10^{-3},10^{-4},10^{-5}$  times of the original concentration, represented by the values of dilution factor collected from CRF in 0, 1, 2, 3, 4, 5. The number of colonies from each plate collected in the CRF will be converted to CFU per mL using the formula: *Number of colonies collected from CRF*  $\times 10^{dilution factor collected in CRF+1$ . Because of the initial 10-fold dilution factor during sputum sample preparation, 1 is added to the power of 10. The CFU value reported from the laboratory is set to missing if the qualitative culture result is "Negative for MTB Complex" or "Contaminated". Because two results are collected per visit, the method to derive the analysis value for CFU for a visit day is described as follows:

If only one CFU result is available, then the available result is used as the CFU/mL value from that visit. If both CFU results are available, the average CFU/mL is taken as the value for that visit. If both sputum samples have missing CFU result, then the qualitative test result from SOLID MICROBIAL CULTURE will be taken into consideration. If both of the SOLID tests are "negative for MTB Complex", or if one of the SOLID results is "negative for MTB complex" and the other is "CONTAMINATED", the CFU for that visit is set to 5 CFU/mL, since the lower detection limit of the agar media is 5 CFU/mL. If both SOLID tests are "CONTAMINATED", then the CFU/mL for that visit is still treated as missing.

The baseline value derived for the analyses is as follows.						

The study day of baseline is set to be 0 no matter whether the baseline comes from Day - 2 or Day -1 or the average. The derived analysis CFU is log10 transformed in the calculations of decline in bacteria load. The early bactericidal activity (*EBA*) is determined by the rate of decline in log10CFU/mL during the first 14 days of treatment. The rate of decline will be estimated using both a two-point calculation (day 14 and day 0 (baseline)) as well as a linear-regression based approach as discussed in Section 8.1.1.1.1 and Section 8.1.1.1.2.

and

Version Date: 16 May 2022

Protocol 323-201-00003

The effect size for EBA for IMP-1 group relative to that of IMP-2 group is expressed as the ratio of EBA as shown in formula (1). Either Fieller's method or Delta method as described in Sections 8.1.1.2  will be used in the estimation of the confidence interval of the ratio

$$\frac{EBA_{0-14,IMP1}}{EBA_{0-14,IMP2}}\tag{1}$$

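### SAP 8.1.1 ignores a culture-negative plate when its partner is positive but counts it otherwise, and its 5 CFU/mL limit does not follow from its conversion formula

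*SAP*

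**What the plan says.** All the rules at issue are in SAP 8.1.1 (Stage 1).

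- Plating: "Two agar media bi-plates will be inoculated with 0.1 mL sputum sample per side (total of 0.2 ml per whole plate) at each visit".
- Conversion: CFU/mL is the colony count times 10 to the power (dilution factor + 1), with dilution factors from 0 to 5. The added 1 is explained as follows: "Because of the initial 10-fold dilution factor during sputum sample preparation, 1 is added to the power of 10".
- Missing counts: "The CFU value reported from the laboratory is set to missing if the qualitative culture result is" negative for MTB complex or contaminated.
- Two counts available: their arithmetic mean is the visit value. One available: "If only one CFU result is available, then the available result is used as the CFU/mL value from that visit".
- No count available: only now is the qualitative result read. Two negatives, or one negative and one contaminated, give 5 CFU/mL, "since the lower detection limit of the agar media is 5 CFU/mL". Two contaminated plates leave the visit missing.

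The log10 is taken after this derivation, and EBA is the fall from baseline (day 0) to Day 14, by a two-point calculation and by a mixed-model slope. SAP 5.4 refers CFU imputation to these sections. Protocol 7.3 says that missing sputum concentrations are not imputed. Neither changes the handling of a positive/negative pair.

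**The concern.** A contaminated plate carries no information about bacterial load; a negative plate does. The rule codes both as missing and recovers the negative result only when no count is left. The same observation is then used or ignored according to what its partner shows, and the SAP gives no reason. For its other assays the SAP keeps results at the limit: LAM below 15 pg/mL becomes 15, and a negative post-baseline MGIT culture becomes 42 days (SAP 8.2).

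The error goes one way at the visit level: dropping the lower of two readings raises the visit value. It can occur only where one plate may plausibly show no growth, that is, at low counts. A Day 14 visit scored too high makes that subject's EBA too small. The variable feeds the Stage 1 primary efficacy endpoint, both EBA estimators, the EBA ratios and the Stage 2 CFU comparisons.

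The second issue is scale. A visit fixed at 5 CFU/mL is compared with counts from the formula, so the two must share a unit. A constant factor in the formula cancels in the log change between two counted visits, but not between a counted baseline and a Day 14 value fixed at 5.

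**Working it through.** **1. How each pairing is scored.** Let c be the positive plate's CFU/mL.

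| Plate A | Plate B | Visit value | Is the negative result used? |
|---|---|---|---|
| negative | negative | 5 | yes |
| negative | contaminated | 5 | yes |
| negative | positive (c) | c | no |

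**2. Excess at a positive/negative visit.**

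- Negative counted as 0: the mean is c/2, so the excess is log10(c) − log10(c/2) = log10(2) = 0.301 at every c.
- Negative counted as the floor of 5: the excess is log10(2c/(c + 5)). At c = 10 it is log10(20/15) = 0.125; at 20, 0.204; at 100, 0.280; at 1000, 0.299.

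Over 14 days the upper value is 0.301/14 = 0.0215 log10/day for that subject. Against the example falls in protocol 7.4.1.1.1, 0.301 is 21% of 1.44 (RHEZ) and 36% of 0.84 (delamanid 200 mg). Those are arm figures, so the percentages only give scale for one affected subject.

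**3. Effect on an arm mean.** The documents give neither Day 14 counts nor the frequency of mixed pairs, so both are assumed. Pairs of plates were simulated with a normal log10 load (SD 1.2), 10 CFU/mL per colony at dilution 0, and plate counts from Poisson to over-dispersed. Bias is the mean log10 value under the SAP rule minus that with the negative plate averaged.

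| Assumed Day 14 mean (log10) | Bias, negative = 0 | Bias, negative = 5 |
|---|---|---|
| 1.0 | 0.05 to 0.07 | 0.03 to 0.04 |
| 2.0 | 0.03 to 0.06 | 0.02 to 0.04 |
| 3.5 | under 0.02 | under 0.02 |

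Mixed pairs were about 11 to 19% of visits at a mean of 2.0. The range 0.02 to 0.07 is 1.4 to 4.9% of a 1.44 fall, or 0.0014 to 0.005 log10/day over 14 days.

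**4. Can the 5 CFU/mL limit be reproduced?** Not from the formula: one colony at dilution 0 gives 1 × 10^(0+1) = 10. Other readings of one colony:

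- 0.2 mL, no initial dilution: 1/0.2 = 5
- 0.1 mL, no initial dilution: 1/0.1 = 10
- 0.2 mL, initial 10-fold dilution: 10/0.2 = 50
- 0.1 mL, initial 10-fold dilution: 10/0.1 = 100

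The value 5 is also the mean of plates at 10 and 0, but the missing-value rule prevents that average. The formula attributes its extra factor of 10 to the initial dilution and names no volume, although 0.1 and 0.2 mL are stated beside it.

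**5. Consequence of the mismatch.** A negative visit fixed at 5 lies log10(10/5) = 0.30 below one colony if a colony is 10 CFU/mL, 1.0 below if it is 50, and 1.3 below if it is 100. Over 14 days these gaps are 0.0215, 0.071 and 0.093 log10/day.

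**The case against.** The strongest reply is that the effect is minor. The 0.30 belongs to one mixed visit and to the convention that negative means 0; with the SAP's floor of 5, the excess at a single colony is only 0.125. The arm-level bias is a few hundredths of a log10. The standard error of a Day 14 mean in 14 subjects with the assumed SD is 1.2/√14 = 0.32, and the trial is not powered for formal comparisons. The documents may also point to higher counts: dilutions run to 10^-5, baseline CFU is tabulated in thousands, and the example falls are 0.84 and 1.44. If baseline were 5 log10 (an assumption), a fall of 1.44 would leave about 3.5, where the bias is under 0.02. The daily figure of 0.0215 applies to the two-point estimate, not to the mixed-model slope.

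All of that stands, and it limits the size of the point. It does not explain why one result is treated in two ways.

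On scale, 5 CFU/mL has a natural reading: one colony in 0.2 mL of undiluted sample. The SAP does not say whether counts are per side or per plate, or whether the recorded dilution factor already includes the 10-fold preparation. That also stands: the mismatch is real, but it does not show which figure is wrong.

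The repair also needs care. If a colony were worth 50 CFU/mL, negatives were averaged as 0 and the floor were set at 50, one colony plus a negative plate would score 25 and an all-negative visit 50. A culture-positive visit would then rank below a culture-negative one.

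**Conclusion.** The point holds as an inconsistency in how the primary CFU variable is derived, with a small expected effect. A positive/negative visit is scored 0.30 log10 too high if a negative plate is 0, or 0.12 to 0.30 too high if it is 5. The arm-level bias is about 0.02 to 0.07 log10 at Day 14 means of 1 to 2, and under 0.02 at 3.5. These figures rest on the assumed means, the SD of 1.2, 10 CFU/mL per colony and the assumed plate variation. The 5 CFU/mL limit does not follow from the formula.

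Two stronger readings are not supported:

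- A reader might infer that the rule shrinks the EBA ratios of the most active regimens. The bias would be largest in arms with low late counts, but the documents do not give the frequency of mixed pairs by arm, so the effect on the ratios is not determined.
- A reader might infer that absolute counts are wrong by a factor of 5, or that the limit of 5 is itself wrong. Values of 5, 10, 50 and 100 CFU/mL per colony are all reachable from the stated figures, and only the laboratory can say which applies.

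The baseline derivation and the technical appendix cannot be read in the public text and are not counted against the plan.

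**What to change.** In SAP 8.1.1:

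1. Set only contaminated plates to missing. Include a negative plate in the visit average in every pairing with a non-contaminated plate, and state the value it takes.
2. Confirm with the microbiology laboratory whether counts are per side or per plate, and whether the recorded dilution factor already includes the 10-fold preparation. Then derive the formula and the limit from the same volume and dilution terms.
3. Assign the floor only when no plate is positive and at least one is negative, at a value no greater than the smallest possible positive visit average. With negatives averaged as 0, that average is half of one colony's value: 5 if a colony is 10 CFU/mL, 25 if it is 50. A culture-positive visit then never ranks below a culture-negative one.

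The cost is a wording change, a small programming change and one laboratory query. No new data are needed.
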